## ABSTRACT

Third molar extraction is a common oral surgical procedure often associated with postoperative pain, edema, and functional limitation. Effective postoperative management plays a key role in minimizing morbidity and promoting patient comfort. Strategies such as cryotherapy may contribute to improved recovery and quality of life after surgery. **Objective:** to investigate the effects of cryotherapy on postoperative outcomes (pain intensity, edema, trismus and quality of life) following mandibular third molar extraction. **Materials and Methods:** This study was designed as a randomized split-mouth clinical trial. The sample consisted of 17 patients (34 mandibular third molars with equivalent levels of impaction) who underwent bilateral surgical extraction. The surgical sites were allocated into two groups according to postoperative care: Group A (control side—without cryotherapy) and Group B (test side—with postoperative cryotherapy using ice packs). All intraoperative and postoperative procedures, instructions, and medications were identical for both groups. Patients were evaluated for pain intensity, trismus severity, presence of edema, and quality of life for up to seven days postoperatively (D7). The evaluator was aware of the postoperative intervention applied. Repeated-measures ANOVA was used to analyze each outcome variable, and associations between continuous variables were assessed using Pearson's correlation test. Statistical significance was set at 5% ( $P < 0.05$ ). **Results:** Overall, postoperative pain intensity was lower in patients who received cryotherapy. Group A reported significantly higher pain intensity on postoperative days 1 and 3. No signs of trismus were observed in Group B at the end of the follow-up period, whereas Group A presented restricted mouth opening at D7. Both groups exhibited edema on postoperative day 2 (D2); however, complete regression of edema by D7 was observed only in Group B. Additionally, a significant association between pain intensity and trismus severity was identified in Group A at D7. Quality-of-life assessment revealed significant differences in three questionnaire items favoring Group B, including greater perceived improvement, better mouth opening, and reduced difficulty sleeping. **Conclusion:** The findings suggest that postoperative cryotherapy is effective in reducing pain intensity and trismus following mandibular third molar extraction. Moreover, this physical therapy modality appears to enhance pain tolerance and patients' self-perceived healing.

**Key-words:** Third Molar; Cryotherapy; Surgery, Oral

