#### **4.4 SAMPLE**

The sample selection consisted on patients referred to the Federal University of Rio Grande do Sul's Dentistry School. The selected patients require bilateral extraction of lower third molars under local anesthesia in two different surgical times. There will be no change to the routine care for patients volunteering in the study. The surgical procedures will be performed by the research team responsible for this study. Participants of both sexes, aged 18 to 50 years, were included in the study if they presented an indication for bilateral surgical removal of mandibular third molars in similar positions according to Pell and Gregory classification. Additional inclusion criteria comprised the absence of systemic comorbidities, local conditions free of inflammatory or infectious processes, no history of allergy to the prescribed medications, and no recent or chronic use of antibiotics, anti-inflammatory drugs, corticosteroids, or analgesics. Participants were excluded from the study if they used medications other than those prescribed by the surgeon, failed to provide the required data, belonged to Group A (control) but used postoperative ice packs, or belonged to Group B (test) and did not use ice packs as instructed by the researchers. There were three dropouts due to noncompliance with postoperative recommendations and the use of non-prescribed medication, resulting in 34 procedures performed in 17 patients.

Postoperative consultations were conducted for follow-up, suture removal, and the evaluation and treatment of any potential postoperative complications.

The selection of the control group and experimental groups were determined by a simple randomization in the immediate postoperative period. One surgical site didn't receive cryotherapy (GA), while the other site received cryotherapy with ice (GB).

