## 4.7 STUDY VARIABLES

The outcome variables of this study were postoperative pain, trismus, local edema, and changes in quality of life following mandibular third molar extraction. Postoperative assessments were performed by the research team, consisting of two calibrated surgeons and one supervising professor, on postoperative days 0 (day of surgery), 2, and 7. The following evaluation protocols were applied:

a) Pain assessment: postoperative pain was assessed using a visual analog scale (VAS– APPENDIX C) ranging from 0 to 10, in which 0 represented no pain, 1–3 mild pain, 3.1–6 moderate pain, and 6.1–10 severe pain. Patients completed the scale at home daily until postoperative day 7.

b) Trismus assessment: trismus was evaluated by measuring maximum mouth opening with the patient seated and the tragus–ala plane parallel to the ground. Patients were instructed to open their mouths three consecutive times, and the mean value was recorded. Measurements were obtained as the interincisal distance in millimeters using a measuring tape. In the absence of maxillary or mandibular incisors, the occlusal edges were used as reference points. Measurements were recorded on postoperative days 0, 2, and 7.

c) Edema assessment: facial edema was measured using the method described by Gabka and Matsumura. Three linear facial measurements were obtained in millimeters with a measuring tape: tragus to pogonion, tragus to oral commissure, and lateral canthus to mandibular angle. The mean of these three measurements was calculated to quantify edema. This assessment was performed preoperatively and on postoperative days 2 and 7.

d) Quality of life assessment: quality of life was evaluated using a questionnaire adapted from the OHIP-14 (APPENDIX D), consisting of 14 dichotomous (yes/no) questions addressing daily functional limitations. The questionnaire included items related to chewing and swallowing ability, dietary changes, alterations in taste, mouth opening, voice changes, speech intelligibility, facial appearance, sleep disturbances, and ability to perform work-related activities. The questionnaire was provided to participants on the day of surgery and completed on postoperative days 0, 2, and 7. At the conclusion of the evaluation period following the second intervention, participants also answered the question: “Which intervention did you perceive as resulting in greater postoperative improvement?”

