## 5.2 TRISMUS

Cryotherapy did not significantly affect maximum mouth opening during the postoperative period ( $F_{(1,16)} = 0.006$ ,  $p = 0.93$ ). However, a significant effect of time ( $F_{(2,32)} = 45.410$ ,  $p < 0.001$ ) and a significant interaction between treatment and time ( $F_{(2,32)} = 4.703$ ,  $p = 0.016$ ) were observed.

Mouth opening decreased on postoperative day 2 compared with baseline in both the control group ( $43.8 \pm 8.9$  vs.  $30.1 \pm 12.2$ ;  $p < 0.001$ ) and the cryotherapy group ( $39.3 \pm 8.8$  vs.  $31.4 \pm 7.9$ ;  $p < 0.01$ ). In Group A, mouth opening remained significantly reduced on postoperative day 7 compared with baseline ( $43.8 \pm 8.9$  vs.  $37.8 \pm 13.6$ ;  $p = 0.005$ ). In contrast, Group B showed recovery of mouth opening by day 7, with values comparable to baseline ( $39.3 \pm 8.8$  vs.  $40.5 \pm 8.5$ ;  $p = 0.43$ ) (Table 2).

[figure not shown]

Table 2: Average of maximal mouth opening values on days 0, 2 and 7 post-op.

Correlation analysis revealed no significant association between pain intensity

and trismus in Group B on postoperative days 2 ( $r = 0.15$ ,  $p = 0.54$ ) or 7 ( $r = 0.11$ ,  $p = 0.66$ ). In contrast, a significant positive correlation was observed in Group A on postoperative day 7 ( $r = 0.62$ ,  $p = 0.005$ ), indicating that greater pain intensity was associated with increased mouth opening restriction. No correlation was found on postoperative day 2 in Group A ( $r = 0.30$ ,  $p = 0.23$ ) (Table 3).

[figure not shown]

Table 3: Correlation between pain and trismus for control group.

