## 5.4 QUALITY OF LIFE

Among the 14 items of the OHIP-14 questionnaire, only three showed significant differences between groups. Regarding mouth opening, 31% of participants in Group A still reported difficulty opening the mouth on postoperative day 7, compared with 23.5% in Group B. Concerning sleep disturbances, Group A showed an approximate 40% reduction in complaints between postoperative days 2 and 7, whereas Group B demonstrated a reduction of approximately 66.6%.

When participants were asked which intervention resulted in greater postoperative improvement, all patients who underwent the control protocol in the first surgery (100%) preferred the cryotherapy intervention. Among those who received cryotherapy during the first procedure, 83% also indicated preference for the cryotherapy side.

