## 7 CONCLUSION

Postoperative cryotherapy was effective in reducing pain intensity and duration, decreasing the need for rescue medication, and shortening the period of mouth opening limitation after mandibular third molar extraction. This intervention also improved patients' perception of recovery and contributed to a more predictable postoperative course. However, cryotherapy did not demonstrate a significant effect on postoperative edema.

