**APPENDIX D – OHIP QUESTIONNAIRE (ORAL HEALTH IMPACT PROFILE)**

	Pre-op	Second day post-op	Seventh day post-op
Did you have difficulty chewing?			
Did you have difficulty swallowing?			
Did you avoid certain foods?			
Have you lost your sense of taste in certain foods?			
Can you open your mouth normally?			
Are you able to taste the food normally?			
Have you noticed any change in your voice?			
Did you have any difficulty speaking?			
Did other people have any difficulty understanding you?			
Has your appearance changed?			
Do you look unusual?			
Are you having trouble sleeping?			
Do you wake up during the night?			
Are you having difficulty performing daily tasks?

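### The abstract's claim of no trismus in Group B at day 7 is not supported, and the claims of a shorter limitation are not demonstrated

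*Combined protocol and SAP*

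**What the plan says.** The Abstract (Results) states: "No signs of trismus were observed in Group B at the end of the follow-up period". Follow-up ended on day 7.

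Section 4.7(b) defines the outcome as a distance: "trismus was evaluated by measuring maximum mouth opening with the patient seated", recorded in millimetres on days 0, 2 and 7. It gives no cut-off for trismus and no rule for calling a patient recovered.

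Section 5.2 reports that "Group B showed recovery of mouth opening by day 7, with values comparable to baseline" (39.3 ± 8.8 vs 40.5 ± 8.5 mm, p = 0.43), while Group A stayed below its baseline (43.8 ± 8.9 vs 37.8 ± 13.6 mm, p = 0.005). The treatment main effect has p = 0.93 and the treatment-by-time interaction p = 0.016.

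Section 5.4 gives the patient-reported result at the same visit: "31% of participants in Group A still reported difficulty opening the mouth on postoperative day 7, compared with 23.5% in Group B". The Appendix D item behind it is "Can you open your mouth normally", answered yes or no.

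The Discussion reads the mouth-opening result as longer-lasting trismus on the control side and cites the questionnaire in support. Section 7 concludes that cryotherapy was effective in "shortening the period of mouth opening limitation after mandibular third molar extraction".

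**The concern.** The abstract makes a statement about patients: none on the cryotherapy side showed the complication at the end. The only measured support is a non-significant comparison of two means. Such a result does not establish absence in a group, still less in each member of it. The trial's own questionnaire, completed at the same visit, points the other way for some patients.

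The duration claims raise a related problem. The length of a limitation is learned from when it ends. Here there were two postoperative measurements, five days apart, and difficulty was still being reported on both sides when observation stopped.

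Trismus is one of the two benefits named in the abstract's conclusion. Someone who reads only the abstract would take it to have been eliminated on the cryotherapy side, when nearly one patient in four there still reported difficulty.

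**Working it through.** **1. The 23.5%.** Section 4.4 describes the final sample as "resulting in 34 procedures performed in 17 patients", so there are 17 sites per group. 4/17 = 23.53%, which reproduces the stated figure exactly. The Clopper-Pearson 95% interval is 6.8% to 49.9%.

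**2. The 31%.** No count out of 17 gives 31%: 5/17 = 29.4% and 6/17 = 35.3%. 5/16 = 31.25% fits, so one Group A answer may be missing. Either way the gap between sides is about one patient (5 vs 4). Fisher's exact test gives p = 0.71 for 5/16 vs 4/17 and p = 1.00 for 5/17 vs 4/17. The exact McNemar test for 5 vs 4 of 17 gives p = 1.00 for every possible pairing.

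**3. What p = 0.43 says about Group B.** Assume a paired t test on 17 patients (16 df).
- Mean change = 40.5 - 39.3 = +1.2 mm.
- Two-sided p = 0.43 corresponds to t = 0.81, so SE = 1.2/0.81 = 1.48 mm.
- 95% CI = 1.2 ± 2.12 × 1.48, or about -1.9 to +4.3 mm.
- SD of individual change = 1.48 × √17 = 6.1 mm.

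If the p-value instead came from the LSD procedure of section 4.8 with a pooled error term on 32 df, the interval is almost the same (about -1.9 to +4.3 mm). The interval describes the mean. With individual changes spread this widely, a mean at baseline is compatible with several patients still restricted.

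**4. The reported ANOVA.** F(2,32) = 4.703 gives p = 0.0162 (stated 0.016). F(1,16) = 0.006 gives p = 0.939 (stated 0.93, which agrees if truncated). The interaction is therefore taken as reported.

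**5. The day 7 comparison between sides.** Section 5.2 does not report one. From its means, the difference is 40.5 - 37.8 = 2.7 mm. With within-patient correlation ρ between sides (not stated, so assumed):

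SD of difference = √(13.6² + 8.5² - 2ρ × 13.6 × 8.5) = √(257.21 - 231.2ρ); t = 2.7/(SD/√17) on 16 df.

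| Assumed ρ | SD (mm) | t | p |
|---|---|---|---|
| -0.2 | 17.4 | 0.64 | 0.53 |
| 0 | 16.0 | 0.69 | 0.50 |
| 0.5 | 11.9 | 0.94 | 0.36 |
| 0.9 | 7.0 | 1.59 | 0.13 |

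To reach p = 0.05 (t = 2.12), ρ would have to exceed about 0.99.

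**6. Where the contrast in change comes from.** Group A changed by 37.8 - 43.8 = -6.0 mm and Group B by +1.2 mm, a contrast of 7.2 mm. Of that, 2.7 mm is the day 7 difference and 4.5 mm is the day 0 difference (43.8 - 39.3). Section 4.5 describes a single baseline taken before the first surgery, section 5.2 reports different day 0 means for the two sides, and the Discussion calls the comparator an immediate postoperative measurement. These three descriptions do not agree.

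**The case against.** The strongest reply is that trismus is the measured distance of section 4.7(b), while the 23.5% comes from a separate quality-of-life item. Self-reported difficulty does not contradict a measured mean that has returned to baseline. Appendix D also has a preoperative column, and no preoperative percentage is given for this item, so the share that is new after surgery is unknown. This stands as a limit: the four answers are not four measured cases of trismus. It does not rescue the abstract sentence, because the measured data do not show absence either, and because the Discussion uses the same questionnaire as corroboration of its trismus result.

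A second reply is that the body of the report is open: section 5.2 speaks of means and section 5.4 prints the 23.5%. That is true, and it makes this a reporting inconsistency, with no data or test in question. The abstract still needs correcting.

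On duration, the reply is that a mean recovered by day 7 on one side and still reduced on the other is a coarse sign of shorter limitation, and that the interaction (p = 0.016) does compare the treatments. Both have some weight. However, the interaction concerns the whole time profile, and more than half of the day 0 to day 7 contrast comes from the unexplained gap at day 0.

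A reader might infer more than the documents support:
- That the duration claim is wrong. The claim is comparative, and 23.5% against 31% points in its favour, so this figure cannot refute it.
- That four Group B patients were physically unable to open normally. Section 5.4 reports perceived difficulty only.
- That the 6.1 mm SD shows how many patients were still restricted by some number of millimetres. The documents set no cut-off, and that SD includes measurement error.

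**Conclusion.** The abstract sentence is not supported and should go. The measured evidence is a mean change of +1.2 mm that did not reach significance, and 4 of 17 Group B patients (23.5%, exact 95% CI 7% to 50%) still reported difficulty at the last visit. The 4/17 follows directly from the reported percentage and sample size. The confidence interval for the mean change rests on reading p = 0.43 as a paired test on 17 patients.

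The statements on shorter duration are not demonstrated; the documents do not show them to be false. They rest on separate tests against baseline within each group. The 2.7 mm day 7 difference is not significant from the stated means and SDs for assumed correlations of -0.2 to 0.9.

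**What to change.** 1. Replace the abstract sentence with one saying that Group B's mean opening at day 7 was not significantly different from its baseline, and that 4 of 17 patients on that side still reported difficulty. Give the Group A count beside it, with the denominator confirmed as 16 or 17.
2. In the Discussion and Conclusion, restrict the duration statements to status at day 7, and say that limitation was not followed to resolution on either side.
3. Report the between-group comparison at day 7 with its confidence interval.
4. Reconcile the baseline across section 4.5, section 5.2 and the Discussion.
5. If per-patient recovery is reported, use that reconciled baseline and a stated tolerance, and label the count as post hoc. With no tolerance it would count noise: under a normal distribution with mean +1.2 and SD 6.1 mm, Φ(-1.2/6.1) = 0.42, or about 7 of 17 Group B patients, would fall below baseline.

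Items 1 and 2 cost rewording and a check of the questionnaire forms. Item 3 is one analysis of measurements already held. Items 4 and 5 require going back to the records to establish what day 0 was. The trismus result will read less favourably.

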#### 4.8 STATISTICAL ANALYSIS

Data normality was assessed using the Kolmogorov–Smirnov test. Parametric analyses were applied to compare groups (control side vs. test side) and postoperative time points (from day 0 to day 7). Continuous variables, including pain intensity (VAS scores), maximum mouth opening (mm), and facial edema (mm), were expressed as means  $\pm$  standard deviation (SD).

A two-way repeated-measures analysis of variance (ANOVA), followed by Fisher's least significant difference (LSD) post hoc test, was used to evaluate the main effects of time and treatment, as well as their interaction, for pain intensity, trismus, and edema. Pain reports were also qualitatively analyzed based on the frequency distribution of pain categories (no pain, mild pain, moderate pain, and severe pain) for both groups.

Associations between pain intensity and trismus or edema were assessed using Pearson's correlation coefficient. Trismus and edema were additionally evaluated using the formulas (Baseline – Postoperative) and (Postoperative – Baseline), respectively. Qualitative data related to quality of life were presented as percentages.

All statistical analyses were performed using SPSS software (version 20.0; IBM Corp., Armonk, NY, USA). Statistical significance was set at  $P < 0.05$ .

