### 5.3 EDEMA

Time significantly affected postoperative edema ( $F_{(2,32)} = 10.34$ ,  $p < 0.001$ ), whereas treatment ( $F_{(1,16)} = 0.516$ ,  $p = 0.48$ ) and the interaction between factors ( $F_{(2,32)} = 1.533$ ,  $p = 0.23$ ) did not.

Both groups exhibited greater edema on postoperative day 2 compared with baseline (Group A:  $123.0 \pm 5.1$  vs.  $126.2 \pm 7.8$ ,  $p = 0.02$ ; Group B:  $123.1 \pm 7.1$  vs.  $126.3 \pm 7.5$ ,  $p = 0.005$ ). No significant differences were observed between baseline and postoperative day 7 in either Group A ( $123.0 \pm 5.1$  vs.  $126.1 \pm 7.8$ ;  $p = 0.86$ ) or Group B ( $123.1 \pm 7.1$  vs.  $123.5 \pm 8.7$ ;  $p = 0.71$ ), indicating resolution of edema by the end of the evaluation period in both groups (Table 4).

[figure not shown]

Table 4: Average of edema values on days 0, 2 and 7 post-op.

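### Group B's non-significant day-7 comparison with baseline is reported as complete regression of edema, but the printed figures do not exclude a partial residual

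*Combined protocol and SAP*

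**What the plan says.** The Abstract (Results) reports that both groups had edema on day 2 and that "complete regression of edema by D7 was observed only in Group B".

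Section 5.3 gives the figures. For Group B, baseline to day 2 is "Group B: $123.1 \pm 7.1$ vs. $126.3 \pm 7.5$ , $p = 0.005", and baseline to day 7 is "Group B ( $123.1 \pm 7.1$ vs. $123.5 \pm 8.7$ ; $p = 0.71". For Group A, baseline to day 7 is "Group A ( $123.0 \pm 5.1$ vs. $126.1 \pm 7.8$ ; $p = 0.86". From the two non-significant day-7 comparisons, 5.3 draws a different conclusion from the Abstract's: "indicating resolution of edema by the end of the evaluation period in both groups". The same section reports no treatment effect (p = 0.48) and no treatment-by-time interaction (p = 0.23).

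The method in 4.8 is "A two-way repeated-measures analysis of variance (ANOVA), followed by Fisher's least significant difference (LSD) post hoc test", with significance at 0.05. Edema (4.7) is the mean of three facial lines in millimetres. Neither 4.7 nor 4.8 defines regression or resolution, sets a margin for residual swelling, or asks for confidence intervals. Section 4.4 gives the number analysed: "resulting in 34 procedures performed in 17 patients".

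**The concern.** A non-significant comparison with baseline shows that a change was not detected. To say that swelling had completely gone is an equivalence-type statement. It needs an interval narrow enough to exclude any residual that would matter, judged against a margin fixed beforehand. The documents give neither, and the Group B day-7 mean is still slightly above baseline.

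At stake is how the Abstract reads on edema, one of the four named outcomes. The sentence contrasts the two sides in favour of cryotherapy, although the direct comparisons in 5.3 are null. Someone who reads only the Abstract could take away an edema benefit that the body of the report does not claim.

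**Working it through.** **Inputs.** All are from 5.3 except n.
- Group B means (SD): baseline 123.1 (7.1), day 2 126.3 (7.5), day 7 123.5 (8.7) mm.
- Group B p-values against baseline: day 2 0.005, day 7 0.71.
- Group A baseline 123.0 (5.1), day 7 126.1 (7.8) mm, p = 0.86.
- n = 17 (4.4), so 16 degrees of freedom for a paired comparison.

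The tests are assumed two-sided; 4.8 does not say.

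**1. Printed edema F tests.** F(2,32) = 10.34 gives p = 0.0003, F(1,16) = 0.516 gives 0.483, and F(2,32) = 1.533 gives 0.231. All agree with 5.3.

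**2. Group B changes.** Day-2 rise = 126.3 - 123.1 = 3.2 mm. Day-7 residual = 123.5 - 123.1 = 0.4 mm. Share of the rise gone = (3.2 - 0.4)/3.2 = 87.5%.

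**3. Standard error implied by p = 0.71.** The p-value cannot be recomputed outright, because the within-patient correlation is not printed. Working backwards, t for two-sided p = 0.71 on 16 df is 0.379, so SE = 0.4/0.379 = 1.06 mm.

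Plausibility check: SE² = (s1² + s2² - 2·r·s1·s2)/17. Solving for r gives (50.41 + 75.69 - 18.98)/123.54 = 0.87. The day-2 comparison (p = 0.005, SE 0.98 mm) implies r = 0.85. The Group B figures are coherent.

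**4. Interval.** 0.4 ± 2.12 × 1.057 = 0.4 ± 2.24, or -1.84 to +2.64 mm. The upper limit is 2.64/3.2 = 83% of the day-2 rise.

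| Variant | Upper 95% limit (mm) |
|---|---|
| 16 df, as printed | 2.64 |
| 32 df (ANOVA error term, as LSD might use) | 2.57 |
| SE from the day-2 comparison | 2.49 |
| Rounding of means (change 0.3 to 0.5) and p (0.705 to 0.715), either df | 1.9 to 3.4 |

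**5. What the test could detect.** Noncentral t on 16 df, noncentrality = true residual/SE, SE = 1.06 mm:

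| True residual at day 7 | Noncentrality | Power | Missed |
|---|---|---|---|
| 1.0 mm | 0.95 | 0.145 | 86% |
| 1.6 mm (half the day-2 rise) | 1.51 | 0.296 | 70% |
| 3.2 mm (all of it) | 3.03 | 0.811 | 19% |

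Over the same rounding (16 df), the miss rate at 1.6 mm runs from 51% (SE 0.78) to 80% (SE 1.35).

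**6. Group A at day 7.** The printed change is 126.1 - 123.0 = 3.1 mm. The SE is largest when r = -1: (5.1 + 7.8)/√17 = 3.13 mm. Then t = 3.1/3.13 = 0.99 and p = 0.34. Any other correlation gives a smaller p, for example 0.19 at r = 0. The printed 0.86 therefore cannot go with these means and SDs.

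**The case against.** The best case for the authors is that the means carry the message: 123.1, then 126.3, then 123.5 mm. A 0.4 mm residual is small, zero lies inside the interval, and the data do not contradict regression. That stands. The 2.6 mm figure is an upper confidence limit, not an estimate, and it depends on a back-calculated standard error. A one-sided 5% bound, the usual choice for an equivalence-type claim, would be lower: about 2.24 mm, or 70% of the day-2 rise.

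A reader might infer three stronger things that the documents do not support:
- **That swelling persisted on the cryotherapy side.** Nothing printed shows this. The estimate points to near-complete return.
- **That the sentence would have appeared whether or not the edema had resolved.** Power against persistence of the full 3.2 mm was about 81%, so that case would probably have been detected. The weakness concerns partial residuals. The documents define no clinically relevant amount, so none can be said to have been missed.
- **That the trial claims an edema benefit in its conclusions.** The Abstract's conclusion names pain and trismus only. Section 6 says edema did not differ significantly between groups, and section 7 says cryotherapy had no significant effect on it.

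The objection does not rescue the word complete, which no interval or margin supports. Nor does it explain why the Abstract limits regression to Group B when 5.3 reports resolution in both groups.

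**Conclusion.** The point holds as one of wording and reporting. For Group B the data are compatible with full return to baseline and also with a partial residual: +0.4 mm, 95% CI about -1.8 to +2.6 mm, upper limit 1.9 to 3.4 mm over rounding. If half the day-2 rise remained, it would go undetected about 70% of the time (51% to 80%). Persistence of the whole rise is unlikely, though at the unfavourable end of rounding the upper limit slightly exceeds 3.2 mm.

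These figures assume that p = 0.71 is a two-sided paired comparison on 17 patients; using the ANOVA error degrees of freedom barely changes the interval.

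The same sentence has a second defect: its restriction to Group B contradicts 5.3. It is tempting to settle this for the Abstract by pointing to Group A's printed +3.1 mm. The documents do not allow that, because the accompanying p = 0.86 is impossible with that mean (at most about 0.34), and they do not show which figure is wrong.

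The consequence is limited, because the overall conclusion on edema is already null.

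**What to change.** 1. In the Abstract and in 5.3, replace the statements of complete regression and of resolution, for both groups, with: *no significant difference from baseline was detected at day 7*. Changing Group B alone would leave 5.3 claiming resolution for Group A, whose printed mean is 3.1 mm above baseline.
2. Report each group's day-7 change from baseline and the between-side difference in change, with 95% confidence intervals computed from the patient data. The back-calculated interval above shows the size of the problem and should not be printed as a result. Put these beside the null treatment (p = 0.48) and interaction (p = 0.23) results.
3. Do not restore the word resolved by adding a margin to 4.8 now. The results are known, so a margin chosen at this stage could not support an equivalence claim.
4. Check Group A's day-7 mean, SDs and p-value against source data, correct whichever is wrong, and then reconcile the Abstract with 5.3.

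The cost is rewording in two places, a few intervals from data already collected, and one source check. The downside is a less favourable sentence in the Abstract; the section 7 conclusion on edema does not change.
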